a) Driving History and Experience Questionnaire DHEQ (Harrison & Fillmore, 2005) This self-report questionnaire gathered information on driving history and behaviors. Included in the questionnaire are measures of driving experience such as length of time holding a driver's license and number of days and miles driven per week. The questionnaire also gathered information about participants driving behaviors, such as license revocations, presence and number of DUI citations and punishments, traffic accidents, traffic tickets, typical driving environment (rural, urban, and interstate), and the type of vehicle transmission (manual, automatic, or both).

b.) Drinking and driving questionnaire (McCarthy et al)This self-report questionnaire gathered information on individuals drinking and driving history. The questionnaire asked participants to respond to questions about drinking and driving history on 4 or 5 point Likert scales. The questionnaire included a measure of frequency of drinking and

driving and typical quantity of alcohol consumed before driving. The items were obtained from a scale reported by McCarthy et al. (2012).

2. Decision making survey

a). the Delayed discounting questionnaire (Senecal et al 2012).

b). Barratt Impulsiveness Scale BIS-11 (Patton et al., 1995)This 30-item self- report questionnaire is designed to measure the personality dimension of impulsivity. Participants rated 30 different statements on a 4-point Likert-type scale ranging from Rarely/Never to Almost Always/Always. Higher total scores indicate higher levels of self-reported impulsiveness (score range 30120).

3. Self-Reported intoxication Survey (attached to the protocol): Includes visual analogue scales which measure self-reports of:

a) Perceived Driver Fitness (Van Dyke and Fillmore 2014)

b) Perceived intoxication and BAC estimation.(Harrison and Fillmore 2005; Harrison et al 2007)

4. Intoxilyzer 8000: The Intoxilyzer breathalyzer is a police grade breathalyzer that has been used in various studies in order to achieve an accurate estimate of BrAC (Fillmore 2001; Harrison and Fillmore 2005;)

5. Smartphone Breathalyzers (Alcohoot, BacTrack, DriveSafe Evoc, Floome, Drink Mate, Keychain Backtrack) These devices were chosen as the only currently commercially available breathalyzers that pair with smartphones, which have received growing attention in the national media. (A smartphone breathalyzer, 2015; Jolly, 2015)

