Approximately 20 men and women, ages 21-39, will be enrolled who self-report as moderate drinkers, who are not seeking treatment for alcohol abuse (i.e. no treatment in the past year and current verbal report of not wanting treatment) do not have alcohol use disorder, as defined by the DSM-V, and do not have any medical conditions that limit or prevent alcohol consumption. Because there are well known risks of alcohol to the unborn fetus, women will be screened with a urine pregnancy test and must confirm a negative result before alcohol is administered. Children will not be recruited for this protocol because alcohol will be administered and the legal drinking age is 21 years. Due to the risks involved with drinking and driving, participants will only be enrolled in the study if they are willing to take public transportation or an uber rideshare home from the study visit.

Subjects will be healthy volunteers, 21-39 years old. They will be non-treatment seeking community drinkers who have previously consumed 4 or more standard drinks of alcohol for women and 5 or more standard drinks of alcohol for men, without problems. Subjects will be included if they drink socially on a drinking level of 4 or more standard drinking days, but excluded if they consume on average 12 or more drinks per week. They will be excluded if they have met criteria for DSM-V (American Psychiatric Association 2013) alcohol or drug dependence (lifetime) or for alcohol or drug abuse currently or in the past 12-months or another major psychiatric disorder,) are using psychotropic medications or are pregnant or nursing. Subjects will undergo a brief medical screening, female subjects will confirm that they are not pregnant using a urine screening.

2. Key Inclusion Criteria:

Inclusion criteria will be: (a) age 21-39 old, (b) Less than 4 drinking days and less than12 drinks per week on average in the past 2 months, (c) have previously consumed four (women) or five (men) or more standard drinks without problems (d) a valid photo ID (e) willing to take public transportation home, via septa or an uber rideshare credit.

3. Key Exclusion Criteria:

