Exclusion criteria will be (a) desire alcohol treatment now or received it in the past 6 months, (b) alcohol dependence with withdrawal per DSM-V criteria and (c) non-English-speaking (d) individuals who have a medical condition or who are taking medication which limits or prevents the consumption of alcohol. We are excluding non-english speaking individuals due to the fact that we do not have translated materials so they will be unable to consent to participate in the study activities. We are also excluding individuals who are under 21 years in age due to legal restrictions of consuming alcohol. We are excluding individuals who have psychological or medical conditions, or are taking medication, that limit or prevent the consumption of alcohol.

4. Subject Recruitment and Screening:

Subjects for this study will be recruited primarily from individuals who present themselves for evaluation for study inclusion by calling our research facility. It is expected that the majority of subjects will volunteer to participate after responding to IRB-approved advertisements on mass transit; and broadcast email messages at institutions (including the University of Pennsylvania Health System) that offer such a service; and by posting/distributing recruitment materials in community settings with public posting areas or other means of providing community access to materials (such as hospitals, town halls, public libraries, YMCAs, health fairs/organizations). We will obtain permission before distributing or posting the approved recruitment materials.

5. Early Withdrawal of Subjects:

During the intake survey participants will be assessed for suicidal ideation and behavior using the Columbia-Suicide Severity Rating Scale. Participants who exhibit suicidal ideation or behavior will be withdrawn from the study and provided resources.

6. Vulnerable Populations:

This study will not include vulnerable populations.

7. Populations vulnerable to undue influence or coercion:

This study may enroll employees or students of Penn. These participants will not be recruited directly or incentivized differently than other subjects in the study. During informed consent study staff will review the voluntary nature of their participation and reminded that they are able to leave the study at any time during the study procedures.

STUDY DESIGN:

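### The final protocol's eligibility sections give different rules for prior alcohol treatment, alcohol use disorder and drinking days, and both exclusion lists omit drug dependence or abuse and nursing

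*Combined protocol and SAP*

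**What the plan says.** The final protocol states eligibility in three places.

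**Target Population and Accrual.** On prior treatment, participants must have "no treatment in the past year and current verbal report of not wanting treatment". On alcohol disorder, they must be people who "do not have alcohol use disorder, as defined by the DSM-V". A later sentence excludes anyone who has met criteria for "alcohol or drug dependence (lifetime) or for alcohol or drug abuse currently or in the past 12-months or another major psychiatric disorder", and those who "are using psychotropic medications or are pregnant or nursing". On drinking frequency: "Subjects will be included if they drink socially on a drinking level of 4 or more standard drinking days".

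**Key Inclusion Criteria and Key Exclusion Criteria.** The inclusion list requires "Less than 4 drinking days and less than12 drinks per week on average in the past 2 months". The exclusion list begins: "Exclusion criteria will be (a) desire alcohol treatment now or received it in the past 6 months, (b) alcohol dependence with withdrawal per DSM-V criteria". Its other two items are not speaking English (c) and a medical condition or medication that limits or prevents drinking (d). An explanatory sentence follows: "We are excluding individuals who have psychological or medical conditions, or are taking medication, that limit or prevent the consumption of alcohol".

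**Methods, Phone Screening.** This section has its own inclusion and exclusion lists, with the same 6-month treatment window, the same dependence-with-withdrawal item, the same items (c) and (d), and the same limit of fewer than 4 drinking days. The screening form is administered and eligibility confirmed at this step. Eligible callers then book the study visit.

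**The concern.** A protocol should give one answer to whether a given caller is eligible. Here two trained staff members relying on different sections could decide differently about the same person, and an enrolment could not be classed clearly as valid or as a deviation.

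Participants receive three doses of alcohol, so the exclusions on alcohol and drug disorder, recent treatment and nursing bear on participant safety. The shorter list is the one printed at the step where eligibility is confirmed. The issue is who is enrolled and given alcohol. It is not a claim that the comparison of devices would be biased.

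**Working it through.** No arithmetic beyond a tally applies, so the check sets the current sections of the final protocol side by side. The summary of changes lists no change to eligibility, and the original protocol has the same wording, so none of this comes from comparing current text with superseded text.

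| Criterion in Target Population | Rule there | Key Exclusion / Key Inclusion lists | Phone Screening lists | Result |
|---|---|---|---|---|
| Prior alcohol treatment | none for 12 months | none for 6 months | none for 6 months | differs |
| Alcohol disorder | no use disorder; no dependence ever; no abuse now or within 12 months | dependence with withdrawal only | dependence with withdrawal only | differs |
| Drinking days | 4 or more, no time unit | fewer than 4 | fewer than 4 | differs |
| Drug dependence or abuse | excluded | not named | not named | absent |
| Nursing | excluded | not named | not named | absent |
| Other major psychiatric disorder | excluded | only if it limits or prevents drinking (explanatory sentence) | not named, beyond item (d) on medical conditions | partly covered |
| Psychotropic medication | excluded | only if it limits or prevents drinking | only if it limits or prevents drinking | partly covered |
| Pregnancy | excluded | not listed | not listed; urine test at the visit | covered by test |

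Tally: 3 differing + 2 absent + 2 partly covered + 1 covered by test = 8. Lifetime alcohol dependence is counted once, within the alcohol-disorder row.

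**Nested conflicts.** The treatment and alcohol-disorder rules are nested. Anyone who passes the Target Population rule also passes the list rule, so applying both gives the narrower Target Population rule. The protocol does not say that both apply.

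**Drinking days.** These rules are not nested. If both counts use the same unit, one requires at least 4 and the other fewer than 4, and no value meets both. If the units differ, the Target Population rule cannot be applied until its unit is stated.

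**Who could pass the written screening list but fail Target Population.**
1. A person treated for alcohol 6 to 12 months ago.
2. A person with alcohol use disorder without withdrawal.
3. A person with drug dependence or abuse.
4. A woman who is nursing.

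**Whether a later step closes the gap.** Study Visit names a screening whose content is not given, a medical history, blood pressure, heart rate, a urine pregnancy test and the suicide-severity scale. Subject Confidentiality mentions a possible meeting with staff to determine eligibility. Neither states a criterion for any of the four groups.

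**The case against.** Four arguments can be made for the protocol as it stands.

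- **The Target Population exclusions are part of the protocol.** Trained staff would be bound by them, and lists headed as key criteria need not be complete. This could explain an omission. It cannot explain one criterion with two values (12 and 6 months) or with opposite directions (at least 4 and fewer than 4). The Phone Screening lists do not carry the word key.
- **The screener appears to ask about the right subjects.** Waiver of Informed Consent says the risk of the screening survey is disclosure of psychiatric and substance use history. So the form probably collects information relevant to the alcohol, drug and psychiatric exclusions. That weakens any assertion that excluded people would get through. But collecting a history does not set an exclusion rule or a look-back, and nothing there concerns nursing. If the form is stricter, it still disagrees with the printed lists.
- **The drinking-days sentence may be garbled.** It follows a sentence about 4 or more drinks and gives no unit, and the summary of changes shows that people did take part, so an empty set was not what was applied. This is fair, and the contradiction is conditional on a shared unit. The sentence still cannot be applied as written.
- **The tally depends on how criteria are grouped.** It does. Drug dependence, for instance, could be read as a psychological condition under the explanatory sentence in Key Exclusion Criteria. That sentence covers only conditions that limit or prevent drinking, and it is missing from Phone Screening.

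What stands is that actual enrolment of excluded people cannot be verified from the documents. The textual conflicts are not answered.

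**Conclusion.** The concern holds. Within the current final protocol, three eligibility criteria have conflicting rules, and two exclusions in Target Population appear in neither exclusion list. Two more are only partly carried over, and pregnancy is covered by testing.

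The textual comparison is certain. The consequence is conditional: the four groups could be enrolled and given alcohol if staff work from the printed Phone Screening list and the unseen screening form does not add the missing criteria. That the drinking-days rules exclude everyone assumes they share one time unit. The number of participants affected cannot be derived from the documents, and no effect on the device-agreement outcome is asserted. The point should be corrected because it concerns who may be given alcohol.

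**What to change.** Reconcile Target Population and Accrual, the Key Inclusion and Key Exclusion Criteria, Phone Screening and the attached screening form into one numbered inclusion and exclusion list. State it once and cross-refer to it elsewhere. The list should give:

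- the look-back for prior alcohol treatment;
- the alcohol and drug use disorder criteria, with their time frames;
- nursing and pregnancy;
- the psychiatric and psychotropic-medication criteria, saying whether they apply outright or only where drinking is limited or prevented;
- the drinking-days rule, with its direction and time unit.

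For each criterion, say whether it is checked on the phone form or at the visit, and in every case before alcohol is given. Which value is right is for the sponsor and investigator to decide.

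The cost is edits to the protocol and screening form, and possibly a few more screen failures.

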This study tests three commercial cellphone breathalyzers (Alcohoot, BacTrack, evoc) and a wearable device that measures blood alcohol content through the skin (BacTrack Skyn) against a police grade breathalyzer device (Intoxilyzer 240)(Test, n.d.). These devices were chosen as the only currently commercially available breathalyzers that pair with smartphones and the only device that moniters alcohol content through the skin. This study will test the accuracy of these smartphone breathalyzers at assessing BrAC against a standard police grade breathalyzer, which is widely used to test BrAC.

In a controlled setting, 30 participants, aged 21-39, will attend a session where they receive 3 doses of a standard amount of alcohol, based on weight and gender(Watson, Watson, & Batt, 1981), designed to raise Blood Alcohol Content to 1.02g/dL. Breath alcohol content (BrAC) will first be measured with each of the three commercial smartphone-paired breathalyzer (Drivesafe Evoc (Drivesafe Evoc, n.d.), Alcohoot(Alcohot Smartphone Breathalyzer, n.d.), BacTrack Pro(BACtrack Mobile Pro, n.d.)) and Intoxilyzer 240. Some participants will be instructed to wear the Bactrack skyn at the beginning of the study). After which, the self-report survey will be administered. The order in which the Breathalyzers are administered will change for each use, per a pre-determined, randomized, order, which only the study staff will have access to. A second dose and third dose will be given and this process will be repeated at 40 minutes and 80 minutes after the first dose. Participants will be blinded to all breathalyzer measurements. A study smartphone will be used to collect smartphone-paired breathalyzer readings. We will also measure self-reported intoxication rating using measures subjective intoxication: Personal Drinking Habits Questionnaire (PDHQ)(Vogel-Sprott, 1992), Perceived Driver Fitness(Van Dyke & Fillmore, 2007) administered by the study staff.

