00 - 10 minutes	• Participant is given a priming dose of alcohol containing vodka in fruit juice designed to raise the BrAC to 0.03-0.04 g/dL based on calculations based on weight and gender

10-30 minutes	Participant rinses with alcohol free mouthwash.
30-40 minutes	 4 measurements of BrAC (Intoxilyzer, Alcohoot, Drivesafe Evoc, Bactrack) Self Report of Intoxication Survey
40-50 minutes	Second dose of alcohol designed to raise BrAC to 0.0708'
50-70 minutes	Participant rinses with alcohol free mouthwash.
70-80 minutes	 4 measurements of BrAC (Intoxilyzer, Alcohoot, Drivesafe Evoc, Bactrack) 2. Self Report of Intoxication Survey
80-90 minutes	 Participant receives third dose of alcohol containing vodka in fruit juice designed to raise the BrAC to 1.01-1.02 g/dL
90-110 minutes	Participant rinses with alcohol free mouthwash.
110-120 minutes	 4 measurements of BrAC (Intoxilyzer, Alcohoot, Drivesafe Evoc, Bactrack) Blood draw to determine Blood Alcohol Content Self Report of Intoxication Survey
135 minutes	 4 measurements of BrAC (Intoxilyzer, Alcohoot, Drivesafe Evoc, Bactrack) Self Report of Intoxication Rating Survey:
150 minutes	 4 measurements of BrAC (Intoxilyzer, Alcohoot, Drivesafe Evoc, Bactrack) Self Report of Intoxication Rating Survey:
175 minutes	 4 measurements of BrAC (Intoxilyzer, Alcohoot, Drivesafe Evoc, Bactrack) Self Report of Intoxication Rating Survey:
190 minutes	 4 measurements of BrAC (Intoxilyzer, Alcohoot, Drivesafe Evoc, Bactrack) Self Report of Intoxication Rating Survey:
205 minutes until study completion	 4 measurements of BrAC (Intoxilyzer, Alcohoot, Drivesafe Evoc, Bactrack) Self Report of Intoxication Rating Survey: Breathalyzer measurements will be obtained until participant is at .03 or lower

* Please note the above table is for participants 1-10. For participants 11-20, the same format will be used but the breathalyzers will be swapped for the following: Backtrack Keychain, DrinkMate, and Floome.

1. Study Instruments:

1. Intake Survey

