Interested participants will call the study hotline where an IRB-approved research assistant or project manager, will answer any questions, administer the study screening and go over the written informed consent. There will be an optional in person study visit for the participant to come in and review study procedures, and sign written informed consent, in person. At the study visit, which occurs at a predetermined time, the participant will first sign written informed consent to participate. They will then take an initial survey, with questions related to their past alcohol use and habits including Driving History and Experience Questionnaire DHEQ1, Drinking and Driving Questionnaire. Participants will also take the Decision making survey, which includes The Barratt Impulsiveness Scale, and the Delayed discounting questionnaire. Some participants will then be instructed to wear the BACtrack skyn wrist device. Participants will then receive three doses of vodka mixed with juice based on their gender and weight designed to reach a peak blood alcohol level of .08 g/dL. After each dose their Breath Alcohol Content (BrAC) will be measured using the three smartphone breathalyzers and the intoxilyzer, measured in a random order. After each breathalyzer measurement, participants will receive the Self-Report of Intoxication Survey, which will include Perceived Driver Fitness and Perceived intoxication and BAC estimation, which are measured using a visual analogue scale.

Besides a preliminary study visit for participants to consent to the study and complete the eligibility survey, all research activities will take place in one of the four CTRC study sites and will occur in a study session of approximately six hours in length with up to four participants at each session for a total of five study sessions. Participants will be separated by curtains and fill out individual paper surveys on paper sheets in order to maintain confidentiality.

Data collection will include contact information, medical history, and history of alcohol use, various measurements of Breath Alcohol Content (BrAC), as well as survey data from the self-reported intoxication survey. The informed consent process during study enrollment will describe all of these aspects of data collection.

5. Data Management:

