Paper forms will be used to collect data and a research assistant will create and maintain the research database. All source documents will be identified by study identification (ID) number, and the key to that ID number will be kept in a locked file cabinet. All personally identifiable information also will be kept separately in a locked file cabinet. No results will be reported in a personally identifiable manner. All tracking system data and research database information will be password-protected with several levels of protection: first, a password will be required to access the computer of the user who has access to the

6. Statistical Analysis Plan:

Primary outcome: Interclass correlation coefficient between smartphone breathalyzer and wearable device readings and the police breathalyzer readings. (See: https://en.wikipedia.org/wiki/Intraclass_correlation).

Secondary outcomes: mean relative differences in breathalyzer and wearable device readings relative to the police breathalyzer with standard deviations. These will be calculated for all measurements and by specific timepoints.

Other secondary analyses: We will conduct descriptive analyses of the association between self-reported measures of intoxication, predicted blood alcohol content, driving fitness, and willingness to drive with measured breath alcohol content by device. We will also explore the effect modification of these by self-reported measures of impulsivity and delay discounting.

RISK/BENEFIT ASSESSMENT:

1. Risks:

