There is some risk that subjects will be identified as participants in the study and that the confidential information provided regarding psychiatric and substance use history will be inadvertently disclosed without the subjects' permission. Urine pregnancy testing is performed for all women of reproductive potential, prior to alcohol administration, to avoid the potential for adverse fetal effects of alcohol. These procedures should add no additional risks beyond the minimal risks normally associated with them.Over a period of 120 minutes, participants will be given three doses of alcohol, which will result in a BrAC of 1.01-1.02g/dL. This amount of alcohol is equivalent to 4-5 standard drinks, an amount that these moderate-drinking subjects have ingested previously. Although the amount of alcohol available to them will produce only moderate blood alcohol levels, subjects could feel intoxicated or react negatively to the alcohol, such as nausea or dehydration. Engaging in any dangerous activities during this period would increase risk of self-harm. Precautions to minimize these risks are discussed below.

After consuming alcohol, participants may be unsafe to operate a vehicle. This risk will be mitigated by providing participants transportation home with either a septa token or rideshare credits for uber of up to \$30, depending on their location. Study activities will be performed in a special clinical research room located in a hospital setting in close proximity to an inpatient care. Nursing and medical personnel will be available to assist in the care of the subject if any adverse event occurs. Participants' breath alcohol concentration (BrAC) and their general condition will be monitored during all aspects of the procedure. The bar-lab will be located in a safe and secure area in in a hospital where medically trained staff will be onsite and there will be ready access to emergency care should it be necessary. All subjects will remain in the test area until their BrAC will be below 0.03 g/dL. All study activities will occur in the afternoon, no earlier than 11am, to minimize nausea and vomiting that could occur with morning alcohol consumption. A meal will be provided.

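### The final protocol gives the same three-dose session two incompatible peak alcohol targets, 1.02 g/dL (1.01-1.02 as BrAC) and .08 g/dL

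*Combined protocol and SAP*

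**What the plan says.** All references are to the final protocol.

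- **STUDY DESIGN:** the three doses, set by weight and gender, are "designed to raise Blood Alcohol Content to 1.02g/dL". The quantity is blood alcohol.
- **METHODS, Timeline, 80-90 minutes:** the third dose is "designed to raise the BrAC to 1.01-1.02 g/dL". The quantity is breath alcohol.
- **RISK/BENEFIT ASSESSMENT, Risks:** the three doses are described as an exposure "which will result in a BrAC of 1.01-1.02g/dL. This amount of alcohol is equivalent to 4-5 standard drinks". The same paragraph says the amount "will produce only moderate blood alcohol levels".
- **METHODS, 4. Administration of Surveys and/or Process:** the three doses are "designed to reach a peak blood alcohol level of .08 g/dL". The quantity is again blood alcohol.

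The earlier steps are given as BrAC. The priming dose aims at 0.03-0.04 g/dL (Dose Administration and Timeline). The 40-50 minute row reads "Second dose of alcohol designed to raise BrAC to 0.0708". That figure may have lost a character when the PDF was read, so it is not counted here as an error.

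The original protocol has the same conflict in the same four sections, and the summary of changes does not mention it.

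**The concern.** One session with one set of doses can have only one intended peak. Here there are two, and both are stated at least once as blood alcohol in the same unit.

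The figure matters because of what depends on it. The protocol specifies dosing by target level, weight, gender and a cited prediction method. Apart from the drink equivalence in Risks, it prints no grams, volumes or formula terms. A reader therefore has only the target against which to check what healthy volunteers are given. Risks also states the higher figure as the level participants will reach, so the exposure statement cannot be relied on.

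There is a lesser scientific consequence. The devices are compared over an induced alcohol range, and the primary outcome is an "Interclass correlation coefficient between smartphone breathalyzer and wearable device readings and the police breathalyzer readings". A coefficient of that kind depends on the spread of the values sampled, so the intended top of the range bears on its interpretation. That top is stated inconsistently.

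**Working it through.** **Inputs**

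| Place in final protocol | Quantity | Target (g/dL) |
|---|---|---|
| STUDY DESIGN | BAC | 1.02 |
| Timeline, third dose | BrAC | 1.01-1.02 |
| Risks | BrAC | 1.01-1.02 |
| Administration of Surveys and/or Process | blood alcohol | .08 |
| Dose Administration and Timeline, first dose | BrAC | 0.03-0.04 |

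The plan gives no dose calculation, so no target can be reproduced. The check is a comparison of printed figures.

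**1. As printed**

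- Blood alcohol against blood alcohol: 1.02/.08 = 12.75; 1.02 - .08 = 0.94 g/dL.
- Lower end of the BrAC range: 1.01/.08 = 12.625; 1.01 - .08 = 0.93 g/dL.

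**2. If the decimal point was misplaced (assumption)**

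- Read as 0.101-0.102: .101/.08 = 1.2625 and .102/.08 = 1.275, a difference of 26-28%.
- Read more loosely as 0.10-0.12: .10/.08 = 1.25 and .12/.08 = 1.5.

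Two distinct targets remain under each reading.

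**3. Size of the third step**

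These are differences between printed targets. They model no elimination, and the .08 column mixes a blood target with a breath target. They show only how far the meaning of the third dose depends on the reading.

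| Second-dose target (assumption) | Third step if peak 1.01-1.02 | if .08 | if 0.101-0.102 |
|---|---|---|---|
| 0.07-0.08 | 1.01 - 0.08 = 0.93 to 1.02 - 0.07 = 0.95 | .08 - .08 = 0 to .08 - .07 = 0.01 | .101 - .08 = 0.021 to .102 - .07 = 0.032 |
| 0.0708, as printed | 0.939-0.949 | 0.009 | 0.030-0.031 |

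The third dose is thus meant to add almost nothing, a modest step or a very large one, depending on which section is read.

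**4. Risks against its own figure**

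Risks equates 1.01-1.02 g/dL with 4-5 drinks. Assume 10-20 g of alcohol per drink, a distribution factor of 0.45-0.75 L/kg and no elimination; none of these is a document figure. The body weight at which the drinks reach 1.01 g/dL is then

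weight (kg) = drinks x grams per drink / (10 x 1.01 x factor).

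- Lowest corner: 4 x 10/(10.1 x 0.75) = 5.3 kg.
- Highest corner: 5 x 20/(10.1 x 0.45) = 22.0 kg.

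Any elimination lowers both weights. Read literally, the figure and the drink equivalence in Risks cannot both describe an adult. This check shows a conflict within Risks. It is not used to choose between .08 and a decimal-shifted reading.

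**The case against.** The strongest reply is that 1.01-1.02 g/dL is plainly a slip. The first dose aims at 0.03-0.04, Risks speaks of moderate levels and 4-5 drinks, and sessions last about 5-6 hours and end at .03 or lower. On this view the 12.75-fold gap is the size of a printing discrepancy, not a difference in anyone's exposure. That stands, and the ratio should be read that way. It does not dispose of the point, because every shifted reading tried above still differs from .08, by a factor of 1.25 to 1.5.

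It is also fair to say that the step sizes rest on an unclear second-dose figure and that the body-weight bound rests on outside assumptions. Neither is needed for the contradiction, which is complete without them. Three of the four sections also agree numerically, so the target is inconsistently stated rather than absent.

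Finally, the consequence is bounded. Risks says "All subjects will remain in the test area until their BrAC will be below 0.03 g/dL", and Dose Administration likewise ties departure to measured levels. The Statistical Analysis Plan works on observed readings, and no effect on a planned analysis has been quantified. These limits are real, but they do not make the exposure statement in Risks accurate.

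**Conclusion.** The concern holds, and the correction is a must-fix. The final protocol gives the same three doses a blood alcohol target of 1.02 g/dL in one section and .08 g/dL in another. The printed gap is 12.75-fold like for like, or 12.6- to 12.75-fold if the 1.01-1.02 BrAC range is included. With the decimal moved to 0.101-0.102 (an assumption), 1.26- to 1.28-fold remains. The comparison as printed needs no assumption.

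The severity rests on two facts: the target defines the dosing in a protocol that prints no dose amounts, and Risks presents it as the expected exposure. It does not rest on any evidence that participants were overexposed; there is none in the documents. It is not concluded here which target was intended.

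**What to change.** Reconcile these places to a single peak target: STUDY DESIGN, the second- and third-dose rows of the Timeline, Administration of Surveys and/or Process, and Risks. Label it consistently as BAC or BrAC, and check it against the dose calculation actually in use. The second-dose row belongs in this because the size of the third step depends on it.

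Then correct the exposure statement in Risks to match, and confirm that the 4-5 drink equivalence and the stated session length are consistent with the reconciled target. No error in either is claimed under .08 or 0.101-0.102. Which target is right is for the sponsor and investigator to establish.

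The cost is a wording correction in four sections by protocol amendment, plus one check against the existing dose calculation. The design, sample size and analyses do not change.
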